### **12 STATISTICAL METHODS AND PLANNED ANALYSIS**

#### **12.1 General Statistical Considerations**

Tabulations of summary statistics, graphical presentations, and statistical analyses will be performed using Statistical Analysis System® software. Descriptive statistics (mean, standard deviation, median, minimum, and maximum) for continuous variables and frequency distributions and percentages for discrete variables will be utilized. All summaries and analyses conducted will be by tumor type, assigned therapy, and combined total subjects. The specifics for these outputs will be described in detail within the Statistical Analysis Plan. The

last pre-administration observation will be used as the baseline value for calculating post-administration changes from baseline. All data entered into the database will be provided in separate data listings showing individual subject values. The planning and reporting of statistical analysis will be carried out as described in the Sponsor's or designee's Standard Operating Procedures governing clinical studies.

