## **12.3 Efficacy Analysis**

Subjects will be evaluated for tumor response, TTR, DOR, and PFS. The ORR will be calculated as the proportion of subjects in the Efficacy Analysis Set who are responders, i.e., BOR=CR and PR; the 95% exact CI for ORR will be calculated. The ORR will be derived using both the RECIST v. 1.1 and the irRECIST v. 1.1, based on the efficacy evaluable subjects in each expansion cohort for each combination therapy.

The DOR, OS, and PFS will be estimated using the Kaplan-Meier methodology.

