1 INTRODUCTION

This Statistical Analysis Plan (SAP) has been developed after review of Kyowa Kirin Pharmaceutical Development, Inc. Protocol 0761-014 (Amendment 2, dated 05 Dec 2016), along with the corresponding electronic case report forms (eCRF). This SAP describes the analysis sets and specific details for the statistical methods to be used for the analysis and reporting of all efficacy, safety, pharmacokinetic parameters, and immunogenicity data collected during the conduct of Protocol 0761-014. This SAP supersedes the statistical considerations identified in Protocol 0761-014 with regards to details of the analyses; where considerations are substantially different, they will be identified as such in this document. In the event that the protocol has amendment(s) that do not have an impact on the statistical analysis methodology, this SAP will not require an amendment. This SAP has been developed and finalized prior to database lock of the clinical database for Protocol 0761-014. If additional analyses are required to supplement the planned analyses described in this SAP, they may be performed and will be identified in the Clinical Study Report (CSR).

This SAP is being written with consideration of the recommendations outlined in the International Conference on Harmonization (ICH) E9 Guideline entitled “Guidance for Industry: Statistical Principles for Clinical Trials” and the most recent ICH E3 Guideline, entitled “Guidance for Industry: Structure and Content of Clinical Study Reports.”

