4.1 General Statistical Considerations

All data collected for the dose finding phase (Phase 1) and the cohort-expansion phase (Phase 2) will be listed. Phase 2 data will be summarized by tumor type and overall (all subjects) if appropriate. All subjects from Phase 1 will be summarized as an independent cohort with all cancer types combined.

Descriptive statistics (mean, standard deviation [Std Dev], median, minimum [Min], and maximum [Max]) will be used for continuous variables; number and percentage of subjects will be used for discrete variables. For change-from-baseline calculations, the last measurement prior to the first dose of IMP will be used as the baseline value.

For summary statistics, the mean and median will be displayed to one decimal place greater than the original values; the standard deviation will be displayed to two decimal places greater than the original values.

All tabulations of summary statistics, graphical presentations, and statistical analyses will be performed using SAS[®] Version 9.4 or higher.

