PR	NE	SD provided minimum criteria for SD duration was met, otherwise, NE
NE	NE	NE

a: If a CR is truly met at first time point, then any disease seen at a subsequent time point, even disease meeting PR criteria relative to baseline, makes the disease PD at that point (since disease must have reappeared after CR). Best response would depend on whether minimum duration for SD was met. However, sometimes ‘CR’ may be claimed when subsequent scans suggest small lesions were likely still present and in fact the patient had PR, not CR at the first time point. Under these circumstances, the original CR should be changed to PR and the best response is PR.

CR=complete response; NE=not evaluable; PD=progressive disease; PR=partial response; SD=stable disease.

Time to Response (TTR)

Time to response will only be summarized descriptively for responders (i.e., CR or PR).

Duration of Response (DOR)

Duration of response will be calculated from the first date of confirmed CR/PR to the date of death or the date of first documented tumor progression (PD), whichever is earlier, using RECIST v1.1. Subjects who remain alive and do not progress will be censored on the date of their last tumor assessment. Subjects who start subsequent therapy without a prior PD will be censored at the last tumor assessment prior to initiation of the subsequent anticancer therapy. Response duration will only be evaluated in subjects with a BOR of CR or PR.

The median DOR, along with its two-sided 95% CI (Brookmeyer, 1982), will be estimated using the Kaplan-Meier (KM) method.

Progression-Free Survival (PFS)

PFS will be calculated as the number of days from the first dose of IMP to the date of death or PD, whichever is earlier. For subjects whose BOR is PR or CR using RECIST v1.1, the date of first documented objective tumor progression or death that occurs after the last documented PR or CR, and prior to the start of post-treatment anti-cancer therapy will be used as the PFS event date. Subjects who die without a reported prior progression will be considered to have progressed on the date of their death. Subjects who remain alive and do not progress will be censored on the last tumor assessment date. Subjects who start subsequent therapy without a prior reported progression will be censored on the date of last tumor assessment prior to initiation of subsequent anticancer therapy. Subjects who have no post-baseline tumor assessments and do not die will be censored on Day 1.

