 Efficacy Analysis Set

All Cancer Types

	Mogamulizumab x mg/kg + Nivolumab 240 mg N=xxx
By RECIST v1.1 (Primary Method [1])	
Time to Response (months)	
N	xx
Mean	xx.x
Std Dev	xx.xx
Median	xx.x
Minimum	xx
Maximum	xx
By RECIST v1.1 (Sensitivity Analysis [2])	
Time to Response (months)	
n	xx
Mean	xx.x
Std Dev	xx.xx
Median	xx.x
Minimum	xx
Maximum	xx

Note: Time to response is calculated from the date of first dose of IMP to the first confirmed Complete Response [CR] or Partial Response [PR] using RECIST v1.1.

[1] The primary method is based on all tumor assessments until the start of subsequent anti-cancer therapy, regardless of progressive disease.

[2] The sensitivity analysis is based on all tumor assessments until the date of progressive disease or the start of subsequent anti-cancer therapy.

Programming note: First page of the table is for "All Cancer Types". Subsequent pages are for NSCLC SQ, NSCLC NSQ PD-L1 non-expressing, Ovarian, CRC, SCCHN, HCC, Pancreatic cancer types separately.

Table 14.2.3.1
 Summary of Duration of Response for Subjects with Best Overall Response of CR or PR
 Efficacy Analysis Set

All Cancer Types

	Mogamulizumab x mg/kg + Nivolumab 240 mg N=xxx
By RECIST v1.1 (Primary Method [1])	
Number of Subjects with CR or PR	N'=xx
Subjects with Progressive Disease/Died (n, %)	xx (xx.x)
Subjects Censored (n, %)	xx (xx.x)
Duration of Response (months)	
Kaplan-Meier Estimate	
25 th Quartile (95% CI)	xx.x (xx.x, xx.x)
Median (95% CI)	xx.x (xx.x, xx.x)
75 th Quartile (95% CI)	xx.x (xx.x, xx.x)
By RECIST v1.1 (Sensitivity Analysis [2])	
Number of Subjects with CR or PR	N'=xx
Subjects with Progressive Disease/Died (n, %)	xx (xx.x)
Subjects Censored (n, %)	xx (xx.x)
Duration of Response (months)	
Kaplan-Meier Estimate	
25 th Quartile (95% CI)	xx.x (xx.x, xx.x)
Median (95% CI)	xx.x (xx.x, xx.x)
75 th Quartile (95% CI)	xx.x (xx.x, xx.x)

Note: Percentage is calculated using N' as the denominator. CR = complete response, PR = partial response. - = Not estimable.
 Duration of response is calculated from the first date of confirmed CR/PR to the date of death or the date of first documented tumor progression, whichever is earlier, using RECIST v1.1.

[1] The primary method is based on all tumor assessments until the start of subsequent anti-cancer therapy, regardless of progressive disease.

[2] The sensitivity analysis is based on all tumor assessments until the date of progressive disease or the start of subsequent anti-cancer therapy.

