Results for individual cancer types are not presented due to the limited number of subjects with Best Overall Response of CR or PR.

Programming note: First page of the table is for "All Cancer Types".

Table 14.2.4.1
 Summary of Progression-Free Survival (PFS)
 Efficacy Analysis Set

All Cancer Types

	Mogamulizumab x mg/kg + Nivolumab 240 mg N=xxx
By RECIST v1.1	
Number of Subjects with PFS Event (n, %)	xx (xx.x)
Earliest Contributing Event:	
Progressive Disease	xx (xx.x)
Death	xx (xx.x)
Number of Subjects Censored (n, %)	xx (xx.x)
Progression-Free Survival (months)	
Kaplan-Meier Estimate of PFS	
25 th Quartile (95% CI)	xx.x (xx.x, xx.x)
Median (95% CI)	xx.x (xx.x, xx.x)
75 th Quartile (95% CI)	xx.x (xx.x, xx.x)
Rate (%) of Being Alive without Progression for at Least [1]	
3 months (95% CI)	xx.x (xx.x, xx.x)
6 months (95% CI)	xx.x (xx.x, xx.x)
9 months (95% CI)	xx.x (xx.x, xx.x)
12 months (95% CI)	xx.x (xx.x, xx.x)
Etc.	

Note: Percentage is calculated using the number of subjects in the column heading as the denominator.

[1] Kaplan-Meier estimate using Kalbfleisch and Prentice method.

Programming note: First page of the table is for "All Cancer Types". Subsequent pages are for NSCLC SQ, NSCLC NSQ PD-L1 non-expressing, Ovarian, CRC, SCCHN, HCC, Pancreatic cancer types separately.

Table 14.2.5.1
 Summary of Overall Survival (OS)
 Efficacy Analysis Set

All Cancer Types	Mogamulizumab x mg/kg + Nivolumab 240 mg N=xxx
Subjects Died (n, %)	xx (xx.x)
Subjects Censored (n, %)	xx (xx.x)
Overall Survival (months)	
Kaplan-Meier Estimate of OS	
25 th Quartile (95% CI)	xx.x (xx.x, xx.x)
Median (95% CI)	xx.x (xx.x, xx.x)
75 th Quartile (95% CI)	xx.x (xx.x, xx.x)
Rate (%) of Being Alive for at Least [1]	
3 months (95% CI)	xx.x (xx.x, xx.x)
6 months (95% CI)	xx.x (xx.x, xx.x)
9 months (95% CI)	xx.x (xx.x, xx.x)
12 months (95% CI)	xx.x (xx.x, xx.x)
Etc.	

Note: Percentage is calculated using the number of subjects in the column heading as the denominator.

[1] Kaplan-Meier estimate using Kalbfleisch and Prentice method.

Programming note: First page of the table is for "All Cancer Types". Subsequent pages are for NSCLC SQ, NSCLC NSQ PD-L1 non-expressing, Ovarian, CRC, SCCHN, HCC, Pancreatic cancer types separately.

Table 14.3.1.1
Overview of Adverse Events
Safety Analysis Set

Adverse Event Category	Mogamulizumab x mg/kg + Nivolumab 240 mg			
	Cycle 1 N=xxx		Any Cycle N=xxx	
	n	(%)	n	(%)
Any TEAEs	xx	(xx.x)	xx	(xx.x)
Any IMP-related	xx	(xx.x)	xx	(xx.x)

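### The SAP's duration of response table is pooled over all tumor types under a fixed footnote, contrary to the by-tumor rule in Protocol 12.1 and without being declared as a departure

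*SAP*

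**What the plan says.** Protocol 12.1 sets the general rule: "All summaries and analyses conducted will be by tumor type, assigned therapy, and combined total subjects". Protocol 12.3 adds the method for the time-to-event measures, "The DOR, OS, and PFS will be estimated using the Kaplan-Meier methodology", without naming a cohort. SAP 4.1 restates the rule with a qualifier: "Phase 2 data will be summarized by tumor type and overall (all subjects) if appropriate". SAP 4.9.1 describes the analysis: "The median DOR, along with its two-sided 95% CI (Brookmeyer, 1982), will be estimated using the Kaplan-Meier (KM) method". It gives no minimum number of responders and no exemption from by-tumor reporting.

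The shell for Table 14.2.3.1 in SAP Section 7 departs from this. Its programming note describes only the all-cancer-types page, and its footnote reads "Results for individual cancer types are not presented due to the limited number of subjects with Best Overall Response of CR or PR". The shell for time to response (Table 14.2.2.1), which covers the same responders, has the usual instruction: "Subsequent pages are for NSCLC SQ, NSCLC NSQ PD-L1 non-expressing, Ovarian, CRC, SCCHN, HCC, Pancreatic cancer types separately". So do the shells for best overall response, its sensitivity version, progression-free survival and overall survival.

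On timing and precedence, SAP Section 1 says "This SAP has been developed and finalized prior to database lock of the clinical database for Protocol 0761-014". It also says that the SAP supersedes the Protocol on analysis details, and that substantial differences will be identified in the SAP.

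**The concern.** DOR is a secondary endpoint, and the expansion cohorts are defined, sized and monitored by tumor type. A pooled Kaplan-Meier median follows whichever tumors respond most and need not describe any one cohort. The assumed historical response rates run from 0% to 25%, so unequal contributions are to be expected.

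The footnote also states its reason as settled fact. A plan can set a rule for small numbers, but here the rule is replaced by its outcome. If a cohort had a dozen or more responders, the shell as written would still withhold its DOR summary.

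**Working it through.** **Step 1: compare the shells.** Six efficacy summary tables are specified: 14.2.1.1, 14.2.1.2, 14.2.2.1, 14.2.3.1, 14.2.4.1 and 14.2.5.1. Five have by-tumor pages; only 14.2.3.1 does not. The time-to-response and DOR tables both cover subjects with a best overall response of CR or PR, so a shortage of responders would affect both equally. The SAP does have a small-group convention, in the shells for the progression-free and overall survival figures: tumor types with more than 10 subjects are plotted. DOR has no corresponding threshold.

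**Step 2: reproduce the plan's figures.** Inputs are the historical rate p0, target rate p1, Stage 1 size n1, total N and futility boundary r1 from SAP Table 1.

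- Total: 32 + 21 + 21 + 29 + 36 + 28 + 17 = 184, as stated.
- Early stopping at the historical rate, PET = P(X ≤ r1 | n1, p0), in table order: 59.8, 34.9, 34.9, 54.0, 52.1, 40.5 and 100%. The SAP states 60, 35, 35, 54, 52, 41 and >99%.

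For hepatocellular carcinoma the SAP boundary of 1 is used. The Protocol table prints 6, which gives 99.9% and not the stated 41%.

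**Step 3: expected responders.** Full enrolment: N × p. With Stage 1 stopping: p × [n1 + (N − n1) × (1 − PET)], where PET is evaluated at the same p.

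Example, head and neck at the historical rate: PET = 0.521, so 0.25 × [14 + 22 × 0.479] = 6.13, against 36 × 0.25 = 9.00 with full enrolment.

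| Cohort | Target, full | Target, stopping | Historical, full | Historical, stopping |
|---|---|---|---|---|
| NSCLC squamous | 12.80 | 12.38 | 6.40 | 4.49 |
| NSCLC non-squamous | 6.30 | 6.21 | 2.10 | 1.72 |
| Ovarian | 6.30 | 6.21 | 2.10 | 1.72 |
| Colorectal | 5.80 | 5.57 | 1.45 | 0.99 |
| Head and neck | 16.20 | 15.57 | 9.00 | 6.13 |
| Hepatocellular | 10.08 | 9.87 | 4.48 | 3.44 |
| Pancreatic | 2.55 | 2.52 | 0 | 0 |
| Total | 60.0 | 58.3 | 25.5 | 18.5 |

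**Step 4: chance of a usable number (full enrolment, exact binomial).** At target rates, P(at least 10 responders) is 0.99 in head and neck, 0.88 in squamous lung and 0.58 in hepatocellular. At historical rates, P(at least 5) is 0.97, 0.80 and 0.47.

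**Step 5: weighting of the pooled estimate.** Squamous lung and head and neck together supply (12.8 + 16.2)/60.0 = 48% of responders at target rates and (6.4 + 9.0)/25.5 = 60% at historical rates, both with full enrolment.

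**The case against.** The strongest defence is that the footnote may prove right. At historical rates with Stage 1 stopping, only head and neck expects 5 or more responders, and most by-tumor Kaplan-Meier medians would be uninformative. That stands as a reason for a threshold on Kaplan-Meier estimates. It does not justify dropping counts and ranges, nor omitting the table when responders are not few.

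It is also true that the data are not lost. Listings 16.2.6.3.1 and 16.2.6.3.2 give each subject's DOR with cancer type and a censoring mark, and Table 14.2.1.1 gives responder counts by tumor. Some non-efficacy shells (infusion times, laboratory values) are pooled only as well. Protocol 12.10 requires departures from the Protocol's analysis to be explained in the study report. These facts limit the harm; they do not remove the inconsistency.

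Four stronger readings are tempting, and the documents do not support them:

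- *Both documents promise by-tumor DOR without condition.* Only Protocol 12.1 does. The closing qualifier in SAP 4.1 most naturally attaches to the overall summary, but it can be read as allowing omission.
- *The omission is data-driven and breaches pre-specification.* The documents do not say. The study is open-label, and the pregnancy-test listing shell shows that some shells were written with knowledge of collected data. Whether this footnote was is unknown, and no test or error rate depends on DOR.
- *The Safety Review Committee would be deprived of DOR at Stage 1.* Its review takes place when Stage 1 enrolment completes, and nothing ties it to this final table.
- *Cohort DOR could not be compared with its benchmark.* The plan gives historical and target figures for response rate only.

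**Conclusion.** The point holds as a stated rule that conflicts with Protocol 12.1, is not identified as a departure as SAP Section 1 requires, and is inconsistent with the time-to-response shell. The conflict with the SAP's own text is softer because of the qualifier in 4.1.

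The stated reason depends on data the plan cannot presume. Expected responders range from about 18.5 (historical rates, Stage 1 stopping) to about 60 (target rates, full enrolment). At target rates with full enrolment, six of seven cohorts expect more than 5 and three expect 10 or more.

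These figures take each cohort's true rate to be exactly its historical or target value. The stopping columns treat the boundaries as binding, although the plan uses them as guidance. They also apply one rate to both Stage 1 responses, which may be unconfirmed, and the confirmed responses used for DOR. The consequence is confined to reporting: a secondary, descriptive endpoint would be summarised only in a form weighted to the tumors that respond most.

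**What to change.** Replace the fixed footnote in Table 14.2.3.1 with a conditional rule, and state it in SAP 4.9.1:

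- For each cohort with at least one responder, add a by-tumor page with the number of responders, events, censored subjects and the range of DOR, marking censored values.
- Add the Kaplan-Meier median and 95% CI when the cohort reaches a minimum responder count that the sponsor states in advance. The documents give no such number for DOR, so the choice is the sponsor's.
- Keep the pooled page as a secondary display.

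If the sponsor prefers pooled results only, the SAP should declare this as a departure from Protocol 12.1 and give its reason.

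The cost is up to seven extra table pages from an existing template. Small cohorts will show wide or non-estimable intervals.

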#### *Hematologic Toxicity*

- 1) Grade 3 thrombocytopenia with clinically significant bleeding;
- 2) Grade 4 thrombocytopenia;
- 3) Febrile neutropenia (absolute neutrophil count  $< 500/\text{mm}^3$  with a single temperature of  $> 38.3^\circ\text{C}$  [ $101^\circ\text{F}$ ]);

- 4) Grade 4 neutropenia of duration > 7 days;

Note: Grade  $\geq$  3 lymphopenia or leukopenia of any duration is not considered a DLT.

*Non-hematologic Toxicity*

- 5) Aspartate transaminase (AST) or alanine transaminase (ALT) elevation  $> 5$  to  $\leq 10$  times the upper limit of normal (ULN) (Grade 3) that does not downgrade to  $\leq$  Grade 1 (or to baseline grade if  $>$  Grade 1 at baseline) within 14 days;
- 6) AST or ALT elevation  $> 10$  times ULN;
- 7) Total bilirubin  $> 5$  times ULN;
- 8) ALT or AST elevation  $> 3$  times ULN AND concomitant total bilirubin  $> 2$  times ULN, without initial findings of cholestasis (elevated serum alkaline phosphatase), AND no other immediately apparent possible causes of ALT/AST elevation and hyperbilirubinemia, including, but not limited to, tumor progression, viral hepatitis, pre-existing chronic or acute liver disease, or the administration of other drug(s) known to be hepatotoxic;
- 9) A  $\geq$  Grade 3 non-hematologic laboratory AE (other than AST, ALT, or bilirubin) is a DLT only if it requires medical intervention or hospitalization. Exception: Grade 3 or Grade 4 electrolyte abnormalities that are not associated with clinical signs or symptoms, and either resolve spontaneously or respond to conventional medical intervention are not DLTs;

Note:  $\geq$  Grade 3 elevation of amylase and/or lipase of any duration not associated with clinical or radiographic evidence of pancreatitis is not a DLT;

- 10) Grade 4 non-hematologic non-laboratory AE;
- 11) Grade 3 skin rash that does not improve to  $\leq$  Grade 2 within 3 days of initiation of maximal supportive care;
- 12) Grade 3 uveitis, bronchospasm, or neurologic toxicity of any duration;
- 13) Any other Grade 3 non-hematologic non-laboratory AE lasting  $> 7$  days, with the following exceptions:
  - a) Grade 3 inflammatory reaction attributed to a local antitumor response (e.g., inflammatory reaction at sites of metastatic disease, lymph nodes, tumor lysis syndrome) is not a DLT;
  - b) Grade 3 fatigue is not a DLT;
  - c) Grade 3 fever not associated with hemodynamic compromise is not a DLT;
- 14) Grade 2 or higher pneumonitis of any duration;

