### **10.3.1 Definitions**

#### **10.3.1.1 Adverse Events**

An AE is defined as any untoward medical occurrence in a patient or clinical investigation subject administered a pharmaceutical product and which does not necessarily have a causal relationship with the treatment. An AE can therefore be any unfavorable and unintended sign (including an abnormal laboratory finding, for example), symptom or disease temporally associated with the use of an IMP (or biologic) whether or not considered related to the IMP.

An AE includes but is not limited to:

- Any clinically significant worsening of a pre-existing condition;
- An AE occurring from overdose of an IMP;
- An AE occurring from abuse (e.g., use for non-clinical reasons) of an investigational or marketed product.

The Investigator will inquire about AEs at all subject visits by asking the subject a non-leading question such as: "How have you been feeling since your last visit?" All AEs, whether observed by the Investigator or reported by the subject, must be collected. The collection of AE and SAE information commences following the subject's written consent to participate in the study. If a subject experiences an AE or SAE, the subject will receive appropriate treatment and supportive care as necessary, and the Investigator will continue to follow up until there is a return to the subject's baseline condition, or until a clinically satisfactory resolution is achieved.

Clinical laboratory abnormalities that qualify as AEs (other than those meeting the definition for serious) and any events that lead to an intervention (including premature discontinuation of IMP or additional concomitant therapy), other than those reported as SAEs, will be reported and evaluated as AEs. Any clinically important changes noted during interim or final physical examinations, 12-lead ECGs, x-rays, or any other potential safety assessments, whether or not these procedures are required by the protocol, must also be recorded.

For this study, disease progression should **not be** reported as an AE. Lymphopenia and leukopenia are expected pharmacologic effects of mogamulizumab and should also **not be** reported as an AE for this study. Lymphocytes and white blood cell counts will be monitored and evaluated with the laboratory data.

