## **12.7 Analyses of Safety Data**

The safety and tolerability of the investigational products are determined by reported AEs, physical examinations, ECGs, vital signs, and laboratory tests. All summaries will be prepared for the entire Safety Analysis Set by tumor type and overall.

All subjects will be assessed regularly for potential occurrence of AEs from the time following the first dose of investigational product until 100 days after the last dose. The CTCAE v4.03 system will be used to grade AEs. Treatment-emergent AEs will be grouped and tabulated by Medical Dictionary for Regulatory Activities preferred terms and system organ class. AEs will be classified by body system, incidence, severity, and causality. All treatment-emergent AEs will be summarized showing the number and percent of subjects for each outcome.

The results from physical examination will be presented in the subject data listings. Vital sign measurements will be summarized at each infusion. The incidence of clinically significant laboratory abnormalities will be presented, and laboratory data will be summarized at each infusion by the CTCAE v. 4.03 toxicity grade. Laboratory data will be presented for subjects having Grade 3 or 4 changes from baseline.

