4.13.2 Clinical Laboratory Evaluation

For chemistry, coagulation and hematology parameters, laboratory measurements (including actual values at the visit and their changes from baseline during the treatment period) will be summarized. In addition, the maximum and minimum post-treatment values will be presented.

Shift tables from baseline to the worst post-baseline values during the treatment period will be provided for chemistry parameters and hematology parameters that have NCI-CTCAE v4.03 toxicity grades. Both scheduled and unscheduled post baseline values during the treatment period will be considered. Additionally, the number and percentage of subjects with Grade ≥ 3 will be presented for each CTCAE gradable laboratory test.

All clinical laboratory data will be listed by subject. Values outside the normal ranges will be flagged and toxicity grades will be displayed for relevant parameters.

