Number (%) of Subjects with Nivolumab-Related Treatment-Emergent Adverse Events (TEAEs) Leading to Nivolumab Discontinuation

By System Organ Class and Preferred Term

Safety Analysis Set

Table 14.3.1.11.3

Number (%) of Subjects with Any IMP Related Treatment-Emergent Adverse Events (TEAEs) Leading to Any IMP Discontinuation
By System Organ Class and Preferred Term
Safety Analysis Set

Table 14.3.1.12

Number (%) of Subjects with Treatment-Emergent Fatal Adverse Events
By System Organ Class and Preferred Term
Safety Analysis Set

Table 14.3.1.13.1

Number (%) of Subjects with Mogamulizumab-Related Treatment-Emergent Fatal Adverse Events
By System Organ Class and Preferred Term
Safety Analysis Set

Table 14.3.1.13.2

Number (%) of Subjects with Nivolumab-Related Treatment-Emergent Fatal Adverse Events
By System Organ Class and Preferred Term
Safety Analysis Set

Table 14.3.1.13.3

Number (%) of Subjects with Any IMP-Related Treatment-Emergent Fatal Adverse Events
By System Organ Class and Preferred Term
Safety Analysis Set

Table 14.3.1.14

Number (%) of Subjects with Treatment-Emergent Infusion Reaction Adverse Events
By Preferred Term
Safety Analysis Set

Table 14.3.2.1
Summary of Clinical Laboratory Values and Change from Baseline During Treatment Period
Safety Analysis Set

All Cancer Types		Mogamulizumab x mg/kg + Nivolumab 240 mg (N=xxx)	
Parameter	Time Point	Actual	Change
Statistic	Statistic		
XXX (Unit)			
Baseline			
n		xx	
Mean		xx.x	
Std Dev		xx.xx	
Median		xx.x	
Minimum		xx	
Maximum		xx	
End of Treatment			
n		xx	xx
Mean		xx.x	xx.x
Std Dev		xx.xx	xx.xx
Median		xx.x	xx.x
Minimum		xx	xx
Maximum		xx	xx
Minimum Post-baseline Value			
n		xx	xx
Mean		xx.x	xx.x
Std Dev		xx.xx	xx.xx
Median		xx.x	xx.x
Minimum		xx	xx
Maximum		xx	xx
Maximum Post-baseline Value			
n		xx	xx
Mean		xx.x	xx.x
Std Dev		xx.xx	xx.xx
Median		xx.x	xx.x
Minimum		xx	xx
Maximum		xx	xx

Continue with other parameters

Programming note: This table is for all cancer types. Display: "All Cancer Types". This table will include all laboratory tests, i.e., hematology, coagulation, and chemistry parameters.

Table 14.3.2.2.1
Shift Table for Laboratory Parameters with Single Direction
Safety Analysis Set

All Cancer Types

Parameter (Unit)	N*	Baseline	Mogamulizumab x mg/kg + Nivolumab 240 mg (N=xxx), n (%)			
			Highest CTCAE Grade During Treatment Period			
			Grade 0	Grade 1-2	Grade 3-4	Total
XXX (Unit)	xx	Grade 0	xx (xx.x)	xx (xx.x)	xx (xx.x)	xx (xx.x)

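### No planned laboratory table separates Grade 4 from Grade 3, so the frequency of Grade 4 lymphopenia and leukopenia, which sites are told not to report as AEs, cannot be read from any table

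*SAP*

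**What the plan says.** Protocol 10.3.1.1 states that "Lymphopenia and leukopenia are expected pharmacologic effects of mogamulizumab and should also" not be reported as an AE in this study, and continues: "Lymphocytes and white blood cell counts will be monitored and evaluated with the laboratory data". The DLT definition in Protocol 6.1.2.1 adds that Grade 3 or higher "lymphopenia or leukopenia of any duration is not considered a DLT".

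For the laboratory data, Protocol 12.7 says that "laboratory data will be summarized at each infusion by the CTCAE v. 4.03 toxicity grade". SAP 4.13.2 plans descriptive summaries and shift tables to the worst post-baseline value, and says that "the number and percentage of subjects with Grade ≥ 3 will be presented for each CTCAE gradable laboratory test".

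SAP section 7 lists three laboratory tables. Table 14.3.2.1 gives descriptive statistics ("This table will include all laboratory tests, i.e., hematology, coagulation, and chemistry parameters"). Tables 14.3.2.2.1 and 14.3.2.2.2 are shift tables under the header "Highest CTCAE Grade During Treatment Period", with Grades 1 and 2 pooled and Grades 3 and 4 pooled for baseline and on-treatment values alike. Listings 16.2.8.1 (chemistry) and 16.2.8.2 (hematology) show the CTCAE grade of each value, subject by subject.

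**The concern.** Safety is the primary endpoint and clinical laboratory evaluations are part of it (Protocol 10.1). The protocol itself calls lymphopenia and leukopenia expected effects of mogamulizumab, so how often they reach Grade 4 is a natural thing to ask of this combination. These are also the two findings that the protocol moves out of AE reporting and into the laboratory data. The laboratory tables would then have to carry the grade, and as designed they do not carry it past a pooled Grade 3-4 band.

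At stake is one safety rate, overall and for each tumor cohort, together with the visibility of one-grade worsening. A move from Grade 1 to 2 or from Grade 3 to 4 stays on the diagonal and reads as no shift.

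**Working it through.** The plan states no figure to reproduce. The check is to follow a Grade 4 lymphocyte or white-cell result through each planned output.

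1. AE tables by highest grade (14.3.1.4 and 14.3.1.5.1 to 14.3.1.5.3). These have separate rows for Grades 1 to 5, but they count reported treatment-emergent AEs. Under Protocol 10.3.1.1 these two findings should not be there.
2. DLT reporting. Protocol 6.1.2.1 excludes them at Grade 3 or above, so they are not captured here.
3. Table 14.3.2.1. It has baseline, end of treatment, minimum and maximum post-baseline values, each with n, mean, SD, median, minimum and maximum. It has no grade counts and is planned for all cancer types only.
4. Tables 14.3.2.2.1 (single direction) and 14.3.2.2.2 (low and high). They are planned overall and by tumor type, with Grade 3-4 as the top band in each direction. The SAP does not say which shell takes lymphocytes and white cells; the result is the same in either.
5. The Grade 3 or above n (%) in SAP 4.13.2. It merges Grades 3 and 4 in the same way, and section 7 lists no separate table for it.
6. Listing 16.2.8.2. It gives the exact grade of each value by subject. It is a listing and gives no frequency.

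Only steps 4 and 5 give graded counts for these tests. Let x be the number in the Grade 3-4 column and g the number at Grade 4. The tables fix x and say only that 0 ≤ g ≤ x. As a percentage, if a share p of subjects is in the pooled band, the Grade 4 share lies between 0 and p. With p = 60%, which is an assumption for illustration and not a figure from the documents, the range is 0% to 60%. The bound has this form for any p.

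Table 14.3.2.1 narrows this a little for the study as a whole. Set against the CTCAE cut-off, the lowest post-baseline minimum shows whether any subject reached Grade 4, and the median of the minima shows whether about half did. It gives no count, and nothing by tumor type.

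For shifts, a subject at Grade 3 at baseline and Grade 4 at worst falls in the cell (3-4, 3-4), the same cell as a subject who stays at Grade 3. The same holds for Grade 1 to Grade 2.

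Against the protocol: section 12.7 calls for summaries by toxicity grade. SAP section 1 says that considerations substantially different from the protocol will be identified in the SAP, and the coarser grouping is not identified as a difference.

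**The case against.** The strongest reply is that this is a display choice. Nothing is lost: Grade 4 cases are counted in the pooled cells and listed individually, and nadir values are summarized in Table 14.3.2.1. For these two findings the protocol attaches no consequence to the grade: they are not DLTs, and Protocol 8.1.2.2 requires no dose delay at any grade. Protocol 12.7 itself speaks of Grade 3 or 4 changes together in its next sentence, and does not say in so many words that each grade needs its own category. Cell depletion is also studied through immune-cell subsets in a separate biomarker report.

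Much of that stands as a limit on the point. It does not supply the missing rate. Listings and nadir statistics are not grade frequencies, the subset data are exploratory, and the sentence in 12.7 on Grade 3 or 4 changes comes in addition to the by-grade summary. That the grade triggers no action here is a reason to expect the information in the laboratory tables, since no other output is designed to carry it.

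The AE exclusion is also less absolute than it looks. Protocol 9.2.2 says that, at minimum, laboratory abnormalities that meet SAE criteria, interrupt or stop study drug, or need corrective therapy are collected as AEs. Some Grade 4 cases could reach Table 14.3.1.4 that way. That would be selective capture and not a Grade 4 rate, and it shows that 9.2.2 and 10.3.1.1 pull in different directions.

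**Conclusion.** The point holds as a reporting gap. No planned laboratory table separates Grade 3 from Grade 4, and for lymphopenia and leukopenia the AE tables are not designed to fill the gap. Their Grade 4 frequency is known from the graded tables only to lie between zero and the pooled Grade 3-4 count, overall and in every tumor cohort. This rests on sites following Protocol 10.3.1.1 and on the shells being programmed as drawn.

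Three stronger readings are not supported. A reader might infer that Grade 4 cases go unreported; they are counted in the pooled cells and listed by subject. A reader might infer that a population all at Grade 3 and one all at Grade 4 would produce the same output; the minimum post-baseline block of Table 14.3.2.1 would differ, although only for all cancer types combined. A reader might cite the protocol's Grade 3 and Grade 4 rules for platelets and neutrophils as evidence of harm; those events are not excluded from AE reporting and can appear by single grade in Table 14.3.1.4.

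No endpoint, decision rule or test changes. It is a low-cost improvement to the reporting of a primary-endpoint safety measure, and worth making.

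**What to change.** In Tables 14.3.2.2.1 and 14.3.2.2.2, replace the row and column bands with Grades 0, 1, 2, 3 and 4, in the low and high directions where both apply. Change both shells, because the SAP does not assign lymphocytes and white cells to one of them. If full splitting makes the tables unwieldy, the minimum is a worst-grade n (%) table for lymphocytes and white cells with a separate Grade 4 row, by tumor type and overall, and a matching sentence in SAP 4.13.2.

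Where any pooling is kept, state in the SAP that it departs from the by-grade summary in Protocol 12.7.

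Reconcile Protocol 9.2.2 with 10.3.1.1, so that it is clear whether a lymphocyte or white-cell abnormality meeting the 9.2.2 conditions is an AE. Which rule should prevail is for the sponsor. The SAP should then say how any such reports are shown.

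Cost: shell and programming changes only. The grade of each value is already assigned for Listings 16.2.8.1 and 16.2.8.2, so no new data are needed. The downside is wider tables with more sparse cells in the smaller cohorts.
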